5 RATIONALE AND BACKGROUND

A. Molecular Diagnostics

Two of the most relevant areas of today's health care diagnostics are "in vivo" imaging and "in vitro" diagnostics. The first includes such technologies as X-Rays, ultrasonic waves, magnetic resonance, or radio-nuclear methods that generate images of the body and its organs. The second areas include tests performed on a sample taken from the body (blood, tissue, sputum, urine, etc.)¹.

Molecular diagnostics belongs to a subset of in vitro diagnostics. It describes a certain type of diagnostic tests that assess a person's health literally at a molecular level, detecting and measuring specific genetic sequences in deoxyribonucleic acid (DNA) or ribonucleic acid (RNA) or the proteins they express. This allows identifying on whether a specific person is predisposed to have a disease, whether they actually have a disease, or whether a certain treatment option is likely to be effective for a specific disease.

Molecular diagnostics has revolutionized biological and biomedical research becoming a growing part of a successful health care system, providing critical information that health care providers and patients need to make the right medical decisions². It often provides objective, quantitative measurements that inform every stage of care—prevention, detection, diagnosis, treatment, and successful management of health conditions.

Personalized medicine, where understanding the underlying molecular mechanisms of diseases allows physicians to evolve to an individual more effective therapy is a derivative of molecular discovery.³ The ultimate power of personalized medicine is the feasibility to treat smaller groups with therapies tailored to their molecular profile.

When specific proteins or genetic sequences have a known association with a specific health condition or disease, they are often referred to as "biomarkers" because they are markers of that condition or disease.⁴ The detection of Cancer biomarkers can be useful in establishing a specific diagnosis and also in establishing a specific diagnosis.

World advances in increasing automation are enabling the development of cutting-edge molecular diagnostics to be performed, better detecting biomarkers and as a result stimulating the understanding the mechanism of diseases that will foster the discovery of the next breakthrough targeted therapies.⁵

Therefore the research around new diagnostics technologies that will enhance the overall effectiveness of therapies in the treated population is essential to increase the proportion of patients with favorable outcomes.

B. Lung Cancer

Non-small cell lung cancer (NSCLC) is a common cause of cancer mortality throughout the world. In 2007, there were 1.5 million new lung cancer cases diagnosed worldwide, including around 733,100 cases in the South American Region.⁶

Approximately 85% of lung cancer is histologically defined as non-small cell and the remaining 14% as small cell. The majority of patients with NSCLC present with inoperable locally advanced (Stage IIIB) or metastatic (Stage IV) disease for which no curative treatment is yet available. In newly diagnosed patients with good performance status, platinum-based doublet-combination chemotherapies are associated with a median overall survival (OS) of 7.4 to 9.9 months.^{7, 8, 9, 10, 11, 12} Therefore, newer agents with novel mechanisms of action are still desperately needed for this serious life-threatening disease.^{15,16}

The rapid and efficient identification of key driver genes in non-small-cell lung cancer (NSCLC) is becoming increasingly important.¹⁷ Clinical screening efforts have revealed that the most common mutations in lung cancer specimens involve *EGFR* and *KRAS*, along with 10 other genes that show a prevalence of mutation in 5% or less of tumors. The *ALK* gene is rearranged in around 3%-5% of patients with NSCLC and has been the focus of intense basic and clinical research, suggesting that the frequency of the gene rearrangement is similar in Asian and Western patients.

ROS1 is a receptor tyrosine kinase of the insulin receptor family. Chromosomal rearrangements involving the *ROS1* gene were originally described in glioblastomas, where *ROS1* (chromosome 6q22) is fused to the *FIG* gene (chromosome 6q22 immediately adjacent to *ROS1*),¹⁶ and have been shown to be transforming in transgenic mice.¹⁷ More recently, *ROS1* fusions were identified as potential driver mutations in an NSCLC cell line (HCC78; *SLC34A2-ROS1*) and an NSCLC patient sample (*CD74-ROS1*).¹⁸ These fusions led to constitutive kinase activity and were associated with sensitivity in vitro and in vivo to crizotinib. As of December 2013, 16 different variants have been found.^{16, 17, 18}

The present study is designed to advance the molecular testing methodologies to identify *ALK+* and *ROS1+* NSCLC patients. Advanced next generation sequencing screening methodologies will be used to identify NSCLC patients whose tumors contain a *ROS1* gene inversion or translocation or an *ALK* translocation.

A parallel test for *ALK+* by either the Abbott *ALK* FISH test or the Ventana *ALK* IHC test is necessary to validate the NGS test in all samples. A parallel test for *ROS1+* by either the Kreatech FISH test or the D4D6 *ROS1* IHC test may be necessary to validate the NGS test in all samples.

6 RESEARCH QUESTION AND OBJECTIVES

This investigation intends to validate molecular diagnostics technologies on ALK+/ROS1+ NSCLC tumor diagnostic; more accurate and precise methods than the existing companion diagnostics (FISH Vysis ALK Break Apart FISH test or the Ventana ALK IHC test).

CEMP Genomic Laboratory together with its sequencing providers (ACC in Brazil, Genoma Mayor in Chile) will process NGS data from tissue and blood and compare it against histopathological and FISH/Ventana ALK results. With this comparison CEMP will be able to determine if NGS technologies are suitable to be considered as accurate diagnostic methods.

The main question that will be addressed in this project is the significant global demand to develop improved molecular diagnostics for cancer, for both translational/clinical applications, as well as companion diagnostics to personalize oncology medicines, in order to increase the overall effectiveness of therapies to patients which may benefit the most, with significant value add to both payers (public healthcare and/or healthcare insurance) and drug manufacturers.

Accordingly, next generation molecular diagnostics should leverage scientific advancements to become less invasive, require less amount of patient tissue for testing and of greater sensitivity to cancer-specific genetic indicators, whether inherited, mutated, or transcribed.

The primary disease focus of this project is to examine novel technologies for NSCLC patient screening for detection of ALK and ROS1 positive patients.

The project will address this technical issue through two research lines:

- 1) Development of an ALK/ROS fusion specific next generation sequencing panel;
- 2) Detection of tumor-derived nucleic acids in the blood of patients diagnosed with NSCLC.

7 RESEARCH METHODS

NGS translocation detection platform

The current study design aims to validate the NGS ALK/RET/ROS detection platform; archival or prospective tumor tissue specimens will be collected from previously diagnosed NSCLC patients enrolled on the study and analyzed for the presence or absence of ALK/RET/ROS translocations.

The data from these assays in combination with the subsequent outcome data collected from the clinical sites will be used to define a diagnostics strategy for the NGS platform.

Circulating nucleic acid (CNA) analyses

For the CNA analysis, two blood tubes will be from all patients at baseline and at time of progression (if possible). One blood tube will be used for RNA analysis. A second blood tube will be used for DNA analysis. Both preparations will be processed and stored frozen until extraction and NGS protocols are defined for this analysis (2016).

Protocols for FFPE processing and blood collection will be provided (See Appendix 1).

Additional tests on the tumor tissue and blood samples can be performed. These may include other tests for the ALK gene fusion or other lung cancer biomarkers according to the state-of-art on this area.

7.1 Study design

This is a non-intervention multi-center study where tissue and blood of NSCLC patients will be collected. Patients will not be treated as part of this protocol and will only participate in the study for the initial samples and clinical parameters collection period.

Up to 6000 patients are expected to be screened in the study overall at 3 or more sites.

Samples should include:

1. Archived or tumor tissue as formalin-fixed paraffin-embedded (FFPE) tissue block or 10 unstained slides containing serial 5-micron tumor tissue sections.
2. Blood samples collected in the provided StepCheck tubes. One 8ml tube for DNA collection, one 8mL tube for RNA collection.

The study will evaluate the strength of NGS technology as diagnostics methods for ALK+ and or ROS1+ tumors.

The strength of the study is based on the fact that NGS technology has an adequate sequencing quality ($Q>30$) and coverage, which ensures the accuracy of results. Given the low prevalence of ALK and ROS rearrangements, it is necessary to sample up to 6000 samples to obtain at least 30 ROS1+ for adequate concordance against other platforms. This is critical for the diagnostic evaluation results, making it eligible as a good diagnostic method.

Besides this, the clinical data will be correlated to the NGS data. This will provide demographics correlations and give information about the incidence of the markers in the Chilean and Brazilian people.

The study will be completed in approximately 48 months.

7.1.1 Inclusion criteria

Patients must meet all of the following inclusion criteria to be eligible for inclusion in the study:

1. Female or male, 18 years of age or older.
2. Patients with histologically or cytological proven diagnosis of NSCLC, pathologically identified as adenocarcinoma.
3. Patient naïve in lung cancer treatment
4. Signed and dated informed consent document indicating that the patient (or legally acceptable representative) has been informed of all the pertinent aspects of the study prior to enrollment.
5. Patients must give consent to the research use of their archived or tumor FFPE tissue, and if available, 2 blood tubes.

7.1.2 Exclusion criteria

Patients meeting any of the following criteria will not be included in the study:

1. Prior chemotherapy treatment.

7.2 Variables

The variables that can impact in the project are non-existence of clinical data, of properly taken samples, misdiagnosis of adenocarcinoma, insufficient blood volume, improper sample storage and transportation, insufficient number of slides for the RNA extraction, inadequate preparation and handling of FFPE, inadequate amounts or bad quality of the RNA derived from FFPE or blood samples, variability in FISH/Ventana ALK testing due the operator or the equipment itself.

7.3 Data sources

The primary data sources for variables relevant to the study objectives will include medical records, patient interviews and molecular profiling.

Data resulting from health or investigator records provided in case report forms will be described under the statistical analysis plan.

7.4 Study size

The results regarding the presence or absence of specific gene fusions (ALK and/or ROS1) after applying NGS will be confirmed using certified and validated test for clinical use, which will allow the specificity of NGS test for the analyzed gene. In all participant subjects the presence of gene ALK and ROS1 variation will be analyzed which will allow to estimate the sensitivity in the NGS test.

The specificity of the NGS trial will be calculated based on cases with a particular gene fusion where a result has been obtained through a certified test. Thus, the specificity will be equal to the confirmed cases through certified test divided by the total of NGS identified mutated cases number. The sensitivity will be calculated dividing the number of cases with a confirmed gene fusion by an ALK and/or ROS1 certified test by the number of the same cases in which the fusion was identified by NGS.

The gene fusion in ROS1 has been selected as the primary variation for the statistical analysis plan, since is the less frequent variation in lung cancer (COSMIC Sanger Database) with a prevalence of 1-2%. The confidence intervals for sensitivity and specificity will be calculated according to the efficiency method of the marker (efficient score method, Newcombe, 1998, Wilson, 1927).^{19, 20}

This study expects to analyze a total of 30 tumors with alterations in the ROS1 gene and 120 alterations in ALK. Thus, for a precision up to 80% (either specificity or sensitivity), will be enough information to establish a sensitivity and specificity estimation of the NGS trial within 0.1 points and 0.05 points (wide of 95% of the confidence interval) respectively.

Given an estimated prevalence of ROS1 at 1-2% and ALK at 3-5% for NSCLC, an initial set of 1000 patients will be screened.

An interim analysis will be performed at the first 1000 NSCLC samples to evaluate prevalence rates. If anticipated prevalence rates do not align with determined prevalence rates at this stage, an additional 2000 patients will be screened for a potential total of 3000 patients.

A subsequent interim analysis will be performed at the 3000 NSCLC samples to evaluate prevalence rates. If anticipated prevalence rates do not align with

determined prevalence rates at this stage, an additional 3000 patients will be screened for a potential total of 6000 patients. The overall screening will occur at 3 or more sites. Patients will only participate in the study for the initial sample collection period.

The study will be completed in approximately 48 months. Since it's a non-interventional multi-center study involving the collection and analysis of FFPE tumor tissue and blood of NSCLC patients, patients will not be treated as part of the protocol.

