The endpoint of this Project will be to analyze 30 positive ROS1 and 120 positive ALK samples to validate the diagnostic method.

Given an estimated prevalence of ROS1 at 1-2% and ALK at 3-5% for NSCLC, an initial set of 1000 patients will be screened. An interim analysis will be performed at the first 1000 NSCLC samples to evaluate prevalence rates (tentatively 10 ROS1+ and 40 ALK+).

For the majority of molecular tests, it is expected that at least 50 positive patient samples be utilized for validation, and ideally at least 10 positives representing each variant being detected¹. Given the low prevalence of ROS1 which has 16 unique variants and recent analysis demonstrating that in 30 ROS1+ patient samples, there is representation of the 3 dominant variants suitable for analytical validation², it is necessary to screen at least 3000 NSCLC samples for identifying positive samples for both ROS1 and ALK that should be sufficient for analytical validation of the NGS platform. If anticipated prevalence rates at the 3000 sample mark do not align with determined prevalence rates at this stage and/or 30 positive ROS1 and 120 positive ALK samples are not obtained, an additional 3000 patients will be screened for a potential total of 6000 patients. The overall screening will occur at 3 or more sites. Patients will only participate in the study for the initial sample collection period.

The study will be completed in approximately 48 months.

Study Treatment

None.

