7.6 Data analysis

Detailed methodology for summary and statistical analyses of data collected in this study will be documented in a Statistical Analysis Plan (SAP), which will be dated, filed and maintained by the sponsor.

The SAP may modify the plans outlined in the protocol; any major modifications of primary endpoint definitions or their analyses would be reflected in a protocol amendment.

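### Protocol 7.4 calls a positive predictive value 'specificity' and inverts sensitivity; for ROS1 no other accuracy definition is visible

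*Protocol*

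**What the plan says.** **Definitions.** Protocol 7.4 (Study size) states that "the specificity will be equal to the confirmed cases through certified test divided by the total of NGS identified mutated cases number". For sensitivity, it takes the cases with a fusion confirmed by a certified ALK and/or ROS1 test and divides them "by the number of the same cases in which the fusion was identified by NGS". SAP 8.1b gives TP/(TP+FN) for sensitivity, TN/(TN+FP) for specificity and TP/(TP+FP) for PPV, all under the comparison of Ventana ALK with NGS for ALK.

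**Role of ROS1.** Protocol 7.4 says "The gene fusion in ROS1 has been selected as the primary variation for the statistical analysis plan". The Abstract says "The endpoint of this Project will be to analyze 30 positive ROS1 and 120 positive ALK samples to validate the diagnostic method", and 7.1 justifies the sample size by the need "to obtain at least 30 ROS1+ for adequate concordance against other platforms". In the SAP, the sample size formulas use ALK prevalence (8.1a). The only tested hypothesis belongs to aim 2, which is ALK (2.2, 4.1). ROS1 appears as prevalence (2.2, 8.2) or incidence (6.3).

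**Reference testing.** Protocol 7.4 says "The results regarding the presence or absence of specific gene fusions (ALK and/or ROS1) after applying NGS will be confirmed" with a certified test. Protocol Section 5 treats the parallel ALK test as required in all samples, but the parallel ROS1 test only as something that might be required.

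**Precedence.** Protocol 7.6 says "The SAP may modify the plans outlined in the protocol", with the condition that "any major modifications of primary endpoint definitions or their analyses would be reflected in a protocol amendment".

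**The concern.** Specificity describes how a test behaves in people without the alteration, so it needs reference-negative samples in its denominator. The protocol's ratio has only NGS-positives there. At a prevalence of 1-2% it can be far below the true specificity, and it would differ between populations even if the assay performed identically in both.

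For ALK the SAP formulas can be taken to govern, so the problem is an inconsistency between two governing documents. For ROS1 nothing visible replaces the 7.4 wording. If an accuracy claim is drawn from the 30 ROS1 positives, the only visible rule would report a prevalence-driven PPV under the name of specificity. If NGS-negative samples are not reference-tested, false negatives and true negatives are unknown, and neither sensitivity nor specificity can be estimated, however the formulas are written. If no ROS1 accuracy claim is intended, the documents should say so, because the Abstract, 7.1 and 7.4 read as if one is.

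**Working it through.** **The plan's own figure.** The only number attached to these definitions is the precision statement in 7.4: 95% intervals within 0.1 (30 ROS1) and 0.05 (120 ALK) at an anticipated 80%. With the Wilson method that 7.4 cites, 30 cases at 0.80 give 0.627 to 0.905 (half-width 0.139), and 120 cases give 0.720 to 0.862 (half-width 0.071). The stated figures are not reproduced as half-widths or as full widths (0.278 and 0.142). That is a separate matter, and nothing below depends on it.

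**Algebra, with the certified test as reference.**

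- Protocol 'specificity' = confirmed / all NGS-positive = TP/(TP+FP). This is the SAP's PPV.
- Protocol 'sensitivity', read literally = reference-positive / those also found by NGS = (TP+FN)/TP = 1/sensitivity. It is never below 1: at true sensitivity 0.80, 0.90 and 0.95 it gives 1.25, 1.11 and 1.05. A Wilson interval for a proportion cannot be applied to it once there is a false negative. If 'confirmed' is instead read as NGS-positive and confirmed, the ratio is TP/TP = 1. A proportion was evidently meant, so this is a wording error.

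**Size of the mislabelling.** With prevalence p, true sensitivity Se and true specificity Sp:

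protocol 'specificity' = Se·p / [Se·p + (1−Sp)(1−p)]

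Inputs: p = 1-2% (ROS1) and 3-5% (ALK), from Protocol 7.4. Assumed, because the documents give no values: Se = 0.90 and Sp = 0.99, 0.995, 0.999.

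| Prevalence | Sp 0.99 | Sp 0.995 | Sp 0.999 |
|---|---|---|---|
| ROS1 1% | 0.476 | 0.645 | 0.901 |
| ROS1 2% | 0.647 | 0.786 | 0.948 |
| ALK 3% | 0.736 | 0.848 | 0.965 |
| ALK 5% | 0.826 | 0.905 | 0.979 |

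Varying Se over 0.80 to 0.95 widens the ROS1 ranges to 0.447-0.906 at 1% and 0.620-0.951 at 2%.

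**Count check.** Take 3000 samples, p = 1%, Se = 0.90, Sp = 0.995. There are 30 reference-positives, giving TP = 27 and FN = 3, and 2970 reference-negatives, giving FP = 14.85 and TN = 2955.15. Protocol 'specificity' = 27/41.85 = 0.645. SAP specificity = 2955.15/2970 = 0.995. Protocol 'sensitivity' = 30/27 = 1.111; SAP sensitivity = 27/30 = 0.900.

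**Which definition applies to which gene.**

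| | Protocol 7.4 | Visible SAP |
|---|---|---|
| ALK accuracy | PPV called specificity; inverted sensitivity | Standard formulas, 8.1b |
| ROS1 accuracy | Same faulty wording | None; prevalence or incidence only |

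**The case against.** The strongest case against is that little of this is live. The SAP settles ALK. The sensitivity inversion is a slip that nobody would compute. No visible SAP analysis estimates ROS1 accuracy, and the protocol's responsibilities section assigns only ALK reference testing to providers. 'Primary variation' stands under Study size, with rarity as the reason, so it may only identify what drives the sample size. The Abstract ties the 30 ROS1 positives partly to representation of the dominant variants. On this reading the residue is a scope mismatch.

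The ALK and sensitivity points stand and are accepted here. The ROS1 point stands in part: the consequence is conditional on an accuracy claim being made. But the Abstract speaks of validating the method, 7.1 of concordance, and 7.4 of sensitivity and specificity for ALK and/or ROS1. Nothing visible withdraws this.

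Protocol 7.4 also says that ALK and ROS1 variation will be analysed in all participants so that sensitivity can be estimated, which can be read as testing regardless of the NGS result. That sentence names no assay. It adds weight to one side of the conflict with Section 5 without resolving it.

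The supplied protocol may also not be the text the SAP was written against. The SAP's study population section cites an amendment 2 of 23 November 2017, while Protocol Section 3 lists none. Part of the objectives is redacted, and SAP appendices 3 to 8, several titled as sample size re-assessments, are shown by title only. This limits confidence on ROS1, but not on the wording of 7.4 or its conflict with SAP 8.1b.

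Finally, the magnitudes rest on assumed accuracy and are driven mainly by the assumed specificity. They show how far the two quantities can part, not a predicted result.

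**Conclusion.** The concern holds and should be fixed. Protocol 7.4 defines specificity as a PPV and inverts the sensitivity ratio; both follow from the text without any assumption. For ALK this is a conflict of definitions, because the SAP formulas are the planned ones; it says nothing about the other ALK analyses.

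For ROS1, the faulty wording is the only visible accuracy definition, and it is unsettled whether NGS-negatives are reference-tested. Under the assumed sensitivity of 0.90 and specificity of 0.99 to 0.999, the reported 'specificity' would be 0.476 to 0.901 at 1% prevalence and 0.647 to 0.948 at 2%. The ROS1 part is held with medium confidence because of the material that cannot be seen.

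**What to change.** 1. In Protocol 7.4, define sensitivity as TP/(TP+FN) and specificity as TN/(TN+FP) against the reference test, and call the confirmed share of NGS-positives PPV.
2. Add one SAP line on ROS1 scope: sensitivity and specificity are claimed only from samples reference-tested regardless of the NGS result. If only NGS-positives are confirmed, report ROS1 PPV alone and state that ROS1 sensitivity and specificity are not claimed.
3. Reconcile Protocol Sections 5 and 7.4 on which samples receive the ROS1 reference test.

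The cost is wording in the protocol and one line in the SAP. If the sponsor regards this as a major change to a primary endpoint analysis, Protocol 7.6 calls for an amendment. The wording itself requires no extra testing, but the ROS1 claim may narrow to PPV. Keeping a ROS1 sensitivity and specificity claim would need reference testing of NGS-negative samples, if that has not already been done.

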4 HYPOTHESES AND DECISION RULES

4.1 STATISTICAL HYPOTHESES

This study have several aims however just the aim 2 has a tested hypothesis.

a. Null Hypothesis (H_0) :

H_0 : “The results of the detection of ALK gene re-arrangements obtained using NGS are not equal to those obtained from using Ventana®”.

b. Alternative Hypothesis (H_1) :

H_1 : “The results of the detection of ALK gene re-arrangements obtained using NGS are equal to those obtained from using Ventana®”.

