8.2 STATISTICAL ANALYSES

This study plan to perform the following statistical analysis:

- 1- Prevalence de ALK and ROS1 mutation
- 2- Concordance between Ventana ALK and NGS ALK assay.

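### Protocol 7.4 makes ROS1 the primary variation for the SAP, but the SAP plans agreement for ALK only, and the documents disagree on which samples get a ROS1 reference test

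*Protocol*

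**What the plan says.** **Protocol.** Section 7.4 says "The gene fusion in ROS1 has been selected as the primary variation for the statistical analysis plan", giving as its reason that ROS1 is the rarer alteration. It continues: "This study expects to analyze a total of 30 tumors with alterations in the ROS1 gene and 120 alterations in ALK". It promises sensitivity and specificity with Wilson-type confidence intervals. Section 7.1 argues that "it is necessary to sample up to 6000 samples to obtain at least 30 ROS1+ for adequate concordance against other platforms". The abstract says "The endpoint of this Project will be to analyze 30 positive ROS1 and 120 positive ALK samples to validate the diagnostic method" and, on the same reasoning, that "it is necessary to screen at least 3000 NSCLC samples". The primary concordance objective in the abstract, however, names only the ALK tests.

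**SAP.** Section 4.1 says "This study have several aims however just the aim 2 has a tested hypothesis"; aim 2 is Ventana ALK against NGS. Section 8.2 lists two analyses: the prevalence of ALK and ROS1, and "Concordance between Ventana ALK and NGS ALK assay".

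**ROS1 reference test.** Protocol section 5 calls the parallel ALK test necessary in all samples, but says of a ROS1 FISH or IHC test that it "may be necessary to validate the NGS test in all samples". Protocol 7.4 says that NGS findings for ALK and/or ROS1, positive or negative, will be confirmed with a certified test.

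**The concern.** A statistician working from the SAP would produce a full set of agreement statistics for ALK and a single proportion for ROS1. The marker that protocol 7.4 calls primary for the SAP, and that protocol 7.1 uses to justify the screening number, would have no validation result. A report saying that NGS is validated for ROS1 would then rest on no planned analysis.

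The second difficulty is the data. Sensitivity needs the cases that NGS missed. Those appear only if NGS-negative samples have a ROS1 reference result, and the documents do not settle whether they will.

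**Working it through.** **1. The plan's own yield.** Inputs are the ROS1 prevalence of 1-2% and ALK prevalence of 3-5% (protocol abstract and 7.4).
- 3000 x 0.01 = 30 ROS1+ and 3000 x 0.04 = 120 ALK+, which are the two targets.
- 1000 x 0.01 = 10 and 1000 x 0.04 = 40, as the abstract states for the first interim look.

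So the ROS1 target follows from 3000 screened at the low end of the ROS1 range.

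**2. Where ROS1 appears in the SAP.**

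| SAP section | Content | ROS1 agreement? |
|---|---|---|
| 2.1.1 workflow | Tissue tested with an ALK FISH or ALK IHC test, plus NGS | No ROS1 test named |
| 2.2 objectives | Concordance for ALK; prevalence for ALK and ROS1 | No |
| 3 interim analyses | Prevalence of both markers | No |
| 4.1 hypotheses | ALK | No |
| 5 populations | Ventana ALK positive and negative | No |
| 6 endpoints | Primary: ALK; section 6.3: ROS1 incidence | No |
| 7 missing values | Patients without ALK data leave the primary analysis | No ROS1 rule |
| 8.1 methods | Sizing formulas defined on ALK prevalence; agreement metrics for ALK | No |
| 8.2 analyses | Prevalence of both; concordance for ALK | No |

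**3. What each testing pattern can estimate.** For ROS1 let a = NGS+/reference+, b = NGS+/reference-, c = NGS-/reference+, d = NGS-/reference-.
- Sensitivity (or positive percent agreement, PPA) = a/(a+c).
- Specificity (or negative percent agreement, NPA) = d/(b+d).
- PPV = a/(a+b).

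If only NGS-positives are reference-tested, c and d are not observed. PPV can be estimated; sensitivity and specificity cannot.

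**4. The formulas in protocol 7.4.** Its specificity is confirmed cases over all NGS-identified cases, a/(a+b), which is PPV. Its sensitivity also divides by cases that NGS identified, so c never enters the denominator. Neither formula matches its name, and neither matches SAP 8.1, which uses TP/(TP+FN) and TN/(TN+FP).

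**5. Illustration of the size.** Assume that only NGS-positives are reference-tested, 3000 patients are screened, 30 are NGS ROS1+ and all 30 are confirmed.
- True cases at 1%: 3000 x 0.01 = 30, so sensitivity = 30/30 = 100%.
- True cases at 2%: 3000 x 0.02 = 60, so sensitivity = 30/60 = 50%.
- Sensitivity of 80% needs 30/0.80 = 37.5 true cases, that is 7.5 missed among 3000 - 30 = 2970 untested negatives (7.5/2970 = 0.25%).

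Nothing in the collected data would separate these cases.

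**6. A separate matter.** With full reference testing, 24/30 has a Wilson 95% CI of 0.627-0.905, a half-width of 0.139 against the 0.1 that protocol 7.4 quotes. That is imprecision at n = 30. The missing analysis does not depend on it.

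**The case against.** Several counterarguments deserve weight.

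- *The ROS1 test is not shown to be optional.* A reader might infer from protocol section 5 that ROS1 reference testing is optional and that missed cases will never be seen. Protocol 7.4 says that both positive and negative NGS results will be confirmed. This stands: the documents conflict, and neither statement can be taken as the rule.
- *Some of what is promised could be produced.* A reader might infer that the ROS1 sensitivity and specificity cannot be delivered at all. On protocol 7.4's own definition, specificity needs only NGS-positives tested. This stands, although that quantity is PPV.
- *ROS1 is not the primary objective.* The visible primary concordance objective is ALK only, and the SAP matches it. The wording in protocol 7.4 sits under study size and could mean only that ROS1 drives the sizing. This is a fair reading, but the sentence refers to the statistical analysis plan, and the paragraphs around it promise accuracy estimates.
- *The screening number is not driven by ROS1 alone.* A reader might infer from protocol 7.1 that up to 6000 patients are screened mainly for ROS1. The abstract also triggers the extension if 120 ALK+ are not reached. At the low prevalences, 30/0.01 = 3000 and 120/0.03 = 4000, so ALK is then the binding target. SAP section 3 also evaluates both prevalences when it sets the sample size; only the formulas in SAP 8.1 are confined to ALK.
- *Not everything is visible.* A block after the primary objectives in the protocol abstract is redacted. SAP appendices 3-8 are listed without content. The SAP cites an amendment 2, while protocol section 3 lists no amendments. Part of the mismatch may be a difference between versions.

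None of these supplies a ROS1 agreement analysis in the body of the SAP.

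**Conclusion.** The mismatch is real. Protocol 7.4 and 7.1 present ROS1 as a marker whose accuracy will be estimated, and the SAP body contains no analysis that does so. Even if every sample received a ROS1 reference test, the SAP as written would not tabulate the results.

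Whether ROS1 sensitivity is estimable is unresolved, because protocol section 5, protocol 7.4 and SAP 2.1.1 do not agree on who is reference-tested. The range of 100% down to 50% is an illustration. It holds if only NGS-positives are tested, all 30 are confirmed, and the true prevalence lies between 1% and 2%.

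The gap does not affect the main ALK concordance analysis. The conclusion is limited to the visible text; ROS1 provisions in the redacted block, the SAP appendices or amendment 2 cannot be ruled out. Protocol 7.6 requires an amendment for major changes to primary endpoint definitions or their analyses, so if the sponsor did narrow the plan to ALK, that should be traceable.

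**What to change.** 1. **SAP 8.2.** Add a ROS1 analysis. In patients with both an NGS and a ROS1 reference result, report PPA and NPA with Wilson 95% CIs. Where only NGS-positives were tested, report PPV and state that sensitivity is not estimable. If some NGS-negatives were tested, say how they were chosen: when positives are tested preferentially, PPA from the tested subset is too high.
2. **Protocol 5 and 7.4, SAP 2.1.1.** Reconcile the statements on which samples receive a ROS1 reference result. Correct the formulas in protocol 7.4 so that sensitivity, specificity and PPV carry their usual meaning and agree with SAP 8.1.
3. **Protocol abstract, 7.1 and 7.4.** Align with the ALK-only primary concordance objective. Limit the ROS1 claim to prevalence plus PPV unless NGS-negatives have reference results.
4. **Versions.** State which protocol amendment the SAP follows.

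The cost is wording in both documents and one extra table. No new testing is needed. The ROS1 claim becomes narrower.
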